## 1.0 BACKGROUND AND HYPOTHESES

Multiple lines of evidence support the role of the subthalamic nucleus (STN) in the motor circuitry, evidenced by its role as a primary target for deep brain stimulation (DBS) in patients with Parkinson's disease (PD). Parkinson's disease can result in progressive deficits in memory, attention, and executive as well as visual-spatial abilities. While STN DBS is associated with a clear motor benefit, its role in cognition has been equivocal with some evidence suggesting cognitive decline in verbal fluency.

It has been increasingly recognized that the STN may contribute to cognitive functions outside the motor circuitry, such as inhibition of automatic or habitual responses. The STN is thought to have three distinct components: motor (dorsolateral STN), associative (ventral) and limbic (ventromedial). While typical DBS stimulation targeting is in the motor (dorsolateral) STN, there is increasing evidence that STN DBS may also affect cognitive domains. For instance, PET studies have demonstrated that DBS of the STN activates the dorsolateral prefrontal cortex, a brain region involved in working memory and executive function, as well as other cortical regions such as the supplementary motor area and the anterior cingulate. Furthermore, prior studies have demonstrated that PD patients with bilateral STN DBS exhibited significant improvements in cognitive functions with stimulation turned "on" versus "off."

Interestingly, these previous studies have all utilized the typical DBS stimulation parameters (high frequency gamma oscillations (100-180 Hz stimulation)). However, there is growing evidence that low frequency (theta: 5-12 Hz) STN stimulation preferentially improves executive function compared to gamma stimulation (100-150 Hz). Such findings are consistent with literature suggesting that theta frequency oscillations in the STN are associated with higher cognitive functions such as conflict resolution. Together, these findings suggest that the STN plays a previously underappreciated role in cognitive functioning. We hypothesize that acute low frequency STN DBS will improve performance on cognitive testing.

This study first aims to confirm previous findings that suggest improvement in cognitive tasks with STN high frequency DBS. Specifically, improvements have been found on the Paced Visual Serial Addition Task (PVSAT), and the Random Number Generation Test (RNGT), which evaluate attention, concentration, task switching, working memory, cognitive processing speed, and executive function. We will also validate the acute effects of DBS on verbal fluency.

To our knowledge, prior studies have not examined the influence of "on" versus "off" stimulation on impulse control. We also propose to examine impulse control, as increased impulsivity is associated with reduced frontal-striatal connectivity in PD patients. Impulsivity will be measured with the Quotient Test, which has been previously used to assess patients with attention-deficit/hyperactivity disorder.

The second aim of this study is to determine if low frequency (theta) stimulation will improve performance on various cognitive tasks more than high frequency stimulation.

Recent findings that suggest theta stimulation improves executive function compared to gamma stimulation raises the possibility that a mix of stimulation frequencies may be required to optimize motor and neurocognitive benefits. This study will directly compare theta versus gamma stimulation to provide further insight into this intriguing possibility.

PD patients with STN DBS electrodes represent a unique opportunity to study this circuitry in humans. Such studies would increase our understanding of role of the basal ganglia in executive and higher cognitive functioning. Confirmation of a direct influence of STN DBS on cognitive function in our patient population would serve as the basis for additional studies that identify the underlying neurophysiological correlates. Our current study has two specific aims: (1) evaluate the acute effects of high frequency (gamma) STN stimulation on cognitive tasks and (2) compare the outcomes to acute effects of low frequency (theta) STN stimulation.

If there is an effect of either stimulation paradigm, future studies would need establish if chronic stimulation would have similar effects. Currently, high frequency stimulation (>100 Hz) is necessary to improve motor outcomes; however, there are known deficits (verbal fluency) after deep brain stimulation. Preliminary data from the PI's previous work as well as published literature demonstrates that various cognitive domains may improve with low frequency (theta; 5-12 Hz) stimulation. Current technology can allow for interleaving stimulation paradigms. Therefore, if low frequency stimulation can improve certain aspects of cognition, it may be possible to interleave high and low frequency stimulation paradigms to improve both the motor and cognitive aspects of Parkinson's Disease with DBS.

## 2.0 OBJECTIVES AND PURPOSE

The first aim of this study is to validate previous neurocognitive changes demonstrated in PD patients with DBS stimulation “on” versus “off” utilizing standard DBS stimulation paradigms. The second aim is to determine if low frequency (theta) stimulation results in improved cognitive performance compared to gamma stimulation. Specifically, we will perform tests that evaluate cognitive processing efficiency, executive function and impulsivity, including the Random Number Generation Test (RNGT), Delis Kaplan Executive Function System (including verbal fluency), Color Word Interference Test (D-KEFS CWIT), and the Quotient Test, respectively. Validation of cognitive improvements at specific stimulation frequencies may lead to identification of stimulation parameters that improve executive function in PD patients. These findings will also serve as the basis for future studies investigating the neurophysiological basis for STN-mediated influences on cognition.

## 3.0 STUDY DESIGN

In this single-center pilot study, we will investigate possible short-term neurocognitive changes induced by deep brain stimulation (DBS) in patients with Parkinson’s disease between the “on” and off” state. During the “on” phase, bilateral monopolar stimulation of the electrode contact associated with the ventral STN will be turned on; testing in the “on” state will be tested at both theta (5-10 Hz) and gamma (100-180 Hz) stimulation. In order to improve blinding to “on” versus “off” states and increase the uniformity of stimulation parameters, the intensity will be adjusted to 2.5 V for all patients. Patients with baseline settings at less than 1.5 V will be excluded from the study. During the “off” phase, both DBS electrodes will be turned off. Since turning the stimulation “on” vs “off” may induce motor effects that could influence testing performance, we will examine if the order in which settings are applied impacts the results of cognitive testing.

During a single outpatient visit, a baseline assessment (baseline stimulation parameters, including frequency, pulse width and voltage) of each neuropsychological task will first be performed in order to accommodate patients to the given task and reduce practice effect. Patients will then perform a battery of tests with the stimulator “on” at the theta frequency, “on” at the gamma frequency, and off; the sequence of these three settings will be changed for each patient in a single-blind fashion. Thus, patients will complete this battery of tasks a total of four times. Duration of testing will be approximately three hours.

The first task to be performed will be the RNGT, which evaluates executive functions such as updating and monitoring of information and inhibition of automatic responses. During this task, participants will be asked to say a sequence of 100 numbers (each number ranging from one to nine) as randomly as possible timed with an auditory pacing stimulus (1 kHz, 200 ms duration) at a rate of 1 Hz. Subjects will be instructed to listen to the first few pacing tones without responding. The loudness of the tone will be adjusted to a comfortable level for each individual. Randomness will be described as picking a piece of paper (numbered one through nine) out of a hat and subsequently replaced. We will analyze previously used measures to quantify deviation from randomness, including repetition measures (repetition of the same digit within a specific time frame), cycling measures (attempt to use all alternative digits before repeating a digit), and seriation measures (tendency to use natural order of numbers).

Executive functioning was also measured with the Delis Kaplan Executive Function System Color Word Interference Test (D-KEFS CWIT). The D-KEFS CWIT test consists of five subtests (verbal fluency, color naming, word reading, color-word interference, and color-word interference switching) subtests. For each subtest the total score consists of the total time in seconds to complete the test as well as the total number of commission and omission errors. The D-KEFS CWIT test has been suggested as a reliable and valid measure of the inhibition and switching aspect of executive functioning in patients with PD.

The Quotient System will be used to measure hyperactivity, attention and impulsivity. It is a noninvasive device designed to capture micro movements of the head using an infrared motion detector in conjunction with a reflector worn on the test subject’s head while the patient completes a 15-20 minute computerized test. The device produces 4 measures of neurocognitive performance: motion analysis, attention analysis, shift in attention state and Quotient composite scores. These tasks are generally used to assess frontal lobe function. After the test is completed, patterns of motion, accuracy of the responses, and fluctuations in attention state are analyzed and scored using proprietary algorithms based on 19 or more parameters. The motion detection includes 6 movement metrics. The Attention Response Analysis includes measures of accuracy, omission errors, commission errors, latency, variability, and response time variability. Baseline movement data will be collected during “on” versus “off” stimulation to ensure that differences in tremor and/or dyskinesia does not

confound interpretation of hyperactivity, attention, or impulsivity. Data for each patient is compared to age and gender matched cohorts.

Data collected from the patients' medical charts will include age, gender, handedness, age at onset of epilepsy, highest level of education, primary language, language laterality, age at surgery, time from diagnosis to surgery medications, other medical conditions, imaging, symptoms, clinical rating scales for Parkinson's disease and previous neuropsychological scores.

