#### **6.0 STRATIFICATION/DESCRIPTIVE FACTORS/RANDOMIZATION SCHEME**

The order of stimulation parameters after baseline will be changed for each patient by moving the order by one step. E.g. patient 1: gamma, theta off; patient 2: theta, off, gamma; patient 3: off, gamma theta. The subject will not be told which setting is being used.

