### 9.0 CLINICAL AND LABORATORY EVALUATIONS AND STUDY CALENDAR

Baseline (Session 1)	Session 2	Session 3	Session 4
RNGT (5 minutes)	RNGT (5 minutes)	RNGT (5 minutes)	RNGT (5 minutes)
Verbal Fluency (5 minutes)	Verbal Fluency (5 minutes)	Verbal Fluency (5 minutes)	Verbal Fluency (5 minutes)
D-KEFS CWIT (10 minutes)	D-KEFS CWIT (10 minutes)	D-KEFS CWIT (10 minutes)	D-KEFS CWIT (10 minutes)
Quotient Task (20 minutes)	Quotient Task (20 minutes)	Quotient Task (20 minutes)	Quotient Task (20 minutes)

(All during one day)

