### 13.0 STATISTICAL CONSIDERATIONS

Based upon our power analyses, our sample sizes for each of the tasks range from 20-29 patients. Therefore, we will enroll 30 patients to detect significant differences in cognitive function for the first phase of the study.

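### Verbal fluency is given four times in one day with no provision for new prompts; if prompts are reused, word recall can shift the setting contrasts in a way the rotation does not cancel

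*Combined protocol and SAP*

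**What the plan says.** Section 3.0 has a baseline assessment at the patient's own settings, then the battery under theta, gamma and off: "Thus, patients will complete this battery of tasks a total of four times". The calendar in section 9.0 lists verbal fluency in all four sessions and adds "All during one day". Neither section says which letters or categories are used, or whether they change between sessions.

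Three features bear on practice and order:

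- The baseline run is meant to accustom patients to the tasks and reduce practice effects (section 3.0).
- The order is rotated (section 6.0): "The order of stimulation parameters after baseline will be changed for each patient by moving the order by one step". The example given is "patient 1: gamma, theta off; patient 2: theta, off, gamma; patient 3: off, gamma theta".
- Section 3.0 intends to examine whether order affects the results. The stated reason is motor effects, and section 13.0 gives no method.

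On sample size, section 13.0 says "our sample sizes for each of the tasks range from 20-29 patients" and sets enrolment at 30. Verbal fluency supplies the 29, from a mean of 47, an SD of 17 and a change of 9.4. The analysis is a within-subjects ANOVA, with no term named for session position or preceding setting.

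**The concern.** Word generation differs from most repeated tasks. A patient given the same letter or category again can repeat words found in the previous session, which section 7.0 implies was about 45 minutes earlier. How many words there are to repeat depends on how well the patient did under the previous setting. This is neither general familiarity with the task nor a residual effect of stimulation, and a longer wait after switching settings would not remove it.

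Part of one setting's gain or loss could then be credited to the setting that follows. The second aim is theta against gamma, and the protocol also wants to validate the acute effect of stimulation on fluency, so both aims use contrasts that could move. Enrolling more patients would not reduce such a shift.

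**Working it through.** **Inputs.** From section 13.0: mean 47, SD 17, change 9.4, projected N 29, enrolment 30. From section 6.0: the three orders. Not in the documents and therefore assumed: two-sided 0.05, 80% power, SD of the within-patient difference 17 (the same as a correlation of 0.5), 47±17 read as a word count, and the carried fraction r.

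**The plan's own figure.** For a paired comparison, n = (17 × (1.96 + 0.84) / 9.4)² gives 26. The exact paired t calculation gives 28, and dividing by 0.955 for a rank test gives 30. The stated 29 lies between the last two, so it reproduces approximately. Power at 30 is 83% by paired t. Other inputs also fit (one-sided 0.05 with 90% power gives 29 or 30), so the plan's assumptions are not uniquely identified.

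**What the rotation balances.** With 30 completers each setting is in each position 10 times, so an equal practice gain per session cancels from every mean contrast. The predecessors are:

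| Setting | gamma-theta-off | theta-off-gamma | off-gamma-theta |
|---|---|---|---|
| Gamma | baseline | off | off |
| Theta | gamma | baseline | gamma |
| Off | theta | theta | baseline |

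Each setting has one fixed study predecessor, in two of the three orders.

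**Size of the shift.** Let G, T and O be the true means, and let a fraction r of the preceding setting's words be repeated. The baseline contribution is the same for all three settings and drops out, leaving:

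- theta-gamma shifts by (2/3) r (G − O)
- theta-off shifts by (2/3) r (G − T)
- gamma-off shifts by (2/3) r (O − T)

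For a difference of 9.4: (2/3) × 0.2 × 9.4 = 1.25 and (2/3) × 0.4 × 9.4 = 2.51 words, which is 13% and 27% of 9.4. For scale, the standard error at 30 patients is 17/√30 = 3.1 words, so the shift is about 0.4 to 0.8 of a standard error.

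| True state | theta-gamma | theta-off | gamma-off |
|---|---|---|---|
| No differences | 0 | 0 | 0 |
| Gamma +9.4, theta = off | +1.3 to +2.5 | +1.3 to +2.5 | 0 |
| Theta +9.4, gamma = off | 0 | −1.3 to −2.5 | −1.3 to −2.5 |
| Both +9.4 | +1.3 to +2.5 | 0 | −1.3 to −2.5 |
| Gamma −9.4, theta = off | −1.3 to −2.5 | −1.3 to −2.5 | 0 |

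**Position left out of the model.** A steady gain of s words per session adds 2s² to the variance of a paired difference under these orders. With s = 3, 4 or 5 the SD becomes √(289 + 18) = 17.5, √(289 + 32) = 17.9 or √(289 + 50) = 18.4. The paired t N rises from 28 to 30, 31 or 33, and power at 30 falls from 83% to 81%, 79% or 77%.

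**The case against.** The strongest reply is that the protocol never says prompts are reused. It repeats the tasks and leaves the items unspecified, and it cites the test manual, which may bear on this. That stands: reuse is the natural reading of a battery given four times, but it is an inference. A reader might conclude that the fluency contrasts are biased; the documents support only that they can be, if prompts repeat.

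A reader might also infer that the baseline run is the only protection. It is not. The rotation removes average practice, and an order check is intended, though without a method.

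Nor do the documents support a general bias in favour of theta. That follows if gamma raises fluency. The protocol's background instead points to fluency decline with stimulation and hypothesises that theta helps. If theta helps and gamma equals off, theta-gamma is untouched in this model and theta-off is understated. What remains is a spurious gamma deficit against off, easily mistaken for the decline the protocol cites.

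The one-session memory is a simplification. With equal carry over two sessions and gamma alone at +9.4, the theta-off shift halves to (1/3) r × 9.4, or 0.6 to 1.3 words, and theta-gamma is unchanged. The word unit is uncertain too: section 3.0 lists verbal fluency among subtests scored by time and errors, while sections 9.0 and 13.0 treat it as its own task.

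Finally, this is a pilot, and the fix leaves the fixed predecessors in place. Both are true. But new prompts stop patients repeating earlier answers, which is the route at issue here.

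**Conclusion.** The concern holds conditionally. The plan gives verbal fluency four times in one day, makes no provision for different prompts, and uses a rotation that balances position but not predecessor. If prompts are reused, recall that depends on the preceding setting stays in the contrasts.

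At r of 0.2 to 0.4 and a 9.4-word difference, the affected contrasts move by 1.3 to 2.5 words. That is less than one standard error at 30 patients, but it is systematic. The figure rests on three assumptions: reused prompts, a word-count score, and a carried fraction for which the documents give no value. The sign depends on which setting helps. The shift is zero if the settings do not differ or r is 0. The sample size of 29 is not called into question by this point.

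**What to change.** In section 3.0, specify a different letter/category set for each session, tied to session number: baseline A, session 2 B, session 3 C, session 4 D. With equal completers per order, the existing rotation then gives each setting each of sets B, C and D equally often. If alternate sets are already intended, a sentence naming them is enough. State the fluency score and its unit in the same place.

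In section 13.0, add session position to the within-subjects model, so that set difficulty and practice do not inflate the error. The term also handles unequal completers: without it, losing three patients from one order at 3 words per session would shift a contrast by up to about 0.7 words. The position term alone would not remove predecessor-dependent recall, so it does not replace the new prompts.

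The cost is three more prompt sheets and no extra testing time. The downside is that the sets will differ somewhat in difficulty. The documents do not show that four comparable sets are available, so the sponsor should confirm this.

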### 12.0 DATA COLLECTION AND MONITORING

RNGT, Verbal Fluency, D-KEFS CWIT task results will be de-identified using a key and collected on paper. They will be stored in a locked cupboard in a locked office. MRNs and the key will be kept on a password protected Excel 2016 (Microsoft) spreadsheet on an encrypted and secure computer. No one except the study personnel will have access to the spreadsheets or papers. The behavioral data collection process is built into the Quotient ADHD System, details of which are described on their website (<http://www.quotient-adhd.com>).

Data collected from patients electronic medical records will be coded and kept on a password protected Excel 2016 (Microsoft) spreadsheet on an encrypted and secure computer separate from the key. No one except the study personnel will have access to the spreadsheets or papers.

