## Power analyses

Study	Projected Sample Size	Mean Result ± SD	Absolute Change (Percent Change)
RNGT	20	43±14	+8.6 (20%)
Delis Kaplan Executive Function	26	9.1±3.3	±1.8 (20%)
Verbal Fluency (preliminary data)	29	47±17	+9.4 (20%)
Quotient	Exploratory		

Non-parametric data analysis will be performed for each of the tasks, including RNGT, D-KEFS CWIT and the Quotient tasks. Each task will be analyzed using within-subjects ANOVA.

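### Does listing verbal fluency as a Color-Word Interference subtest leave a powered outcome without a usable score?

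*Combined protocol and SAP*

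**What the plan says.** Section 3.0 introduces the Delis-Kaplan Color Word Interference Test (CWIT) with this sentence: "The D-KEFS CWIT test consists of five subtests (verbal fluency, color naming, word reading, color-word interference, and color-word interference switching) subtests". The scoring rule follows at once: "For each subtest the total score consists of the total time in seconds to complete the test". Counts of both kinds of error are added to the time.

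Elsewhere verbal fluency stands alone:

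- Section 9.0 gives it its own row, "Verbal Fluency (5 minutes", in all four sessions, next to a 10-minute CWIT row.
- Section 12.0 lists it as a separate result: "RNGT, Verbal Fluency, D-KEFS CWIT task results will be de-identified using a key and collected on paper".
- The power table in Section 13.0 has a row headed "Verbal Fluency (preliminary data" (N 29; 47±17; +9.4, 20%), apart from the Delis-Kaplan row (N 26; 9.1±3.3; ±1.8, 20%).

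Section 1.0 makes it a study target: "We will also validate the acute effects of DBS on verbal fluency". The analysis statement is general: "Each task will be analyzed using within-subjects ANOVA".

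**The concern.** Verbal fluency is one of three outcomes with a projected sample size, and its 29 is the largest, at the top of the 20 to 29 range behind the enrolment of 30. Section 1.0 also names it as a known deficit after deep brain stimulation. The only scoring rule that reaches it does so through its place in the CWIT list, and three other parts of the document do not support that place.

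Read literally, Section 3.0 would have a time-and-error quantity recorded for verbal fluency, and nothing connects such a quantity to 47±17. If verbal fluency is a separate test, no sentence defines its score or says whether higher is better. An undefined score could be chosen after the data are seen. It could also have a different spread from the one used for planning.

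**Working it through.** **1. The plan's own figure.** The inputs are the verbal fluency row of the power table: mean 47, SD 17, change 9.4. The change is 9.4/47 = 0.20, as stated. The standardised change is 9.4/17 = 0.553. The plan gives no alpha, power or within-patient correlation. I assume two-sided alpha 0.05, power 80%, and the tabled SD as the SD of the paired difference.

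- Normal formula: n = ((1.960 + 0.842)/0.553)² = 25.67, so 26.
- Paired t-test: n = 27.65, so 28.
- Paired t-test with the usual 0.955 efficiency allowance for a signed-rank test: 27.65/0.955 = 28.96, so 29, the stated figure.
- Power by paired t-test: 82.0% at 29 patients and 83.3% at 30.

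The 29 is therefore reachable under ordinary assumptions. The same variant does not reproduce all three rows: the random number generation row (stated 20) and the Delis-Kaplan row (stated 26) lie closer to the normal formula, at 20.80 and 26.38. The agreement is only a plausibility check. The calculation uses just the ratio 9.4/17, so moving verbal fluency into or out of the CWIT list leaves it untouched.

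**2. Which reading the document supports.**

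| Place | Verbal fluency is |
|---|---|
| Section 3.0 | one of five CWIT subtests |
| Section 2.0 | in parentheses after the Delis-Kaplan system, with the CWIT named next |
| Section 9.0 | a row of its own |
| Section 12.0 | a recorded result of its own |
| Section 13.0, power table | a row of its own |
| Section 13.0, analysis text | not named; the list of tasks is open-ended |

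The calendar adds up with verbal fluency separate: 5 + 5 + 10 + 20 = 40 minutes a session, and 4 × 40 = 160 minutes a visit. Without its own slot the total would be 4 × 35 = 140 minutes. Both fit the approximate three hours in Section 3.0, so the total does not decide the matter; the separate rows do.

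Section 3.0 prints five labels for a count of five, and four remain if verbal fluency is removed. The count and the list therefore share one slip: the CWIT was named where the wider system was meant. Section 2.0 has the grouping that Section 3.0 appears to have compressed.

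**3. Whether a rival scoring rule exists.** None does. Sections 9.0, 12.0 and 13.0 say where verbal fluency sits, not how it is scored. Section 3.0 cites the examiner's manual (reference 17), whose title covers the whole Delis-Kaplan system. Its content cannot be checked from these documents.

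**4. Whether missing units and direction are peculiar to verbal fluency.** They are not. No row of the power table has a unit or a stated direction of benefit. The random number generation row (43±14, +8.6) also carries a plus sign, although Section 3.0 describes its measures as departures from randomness. The Delis-Kaplan row is not tied to seconds or to errors. The omission runs through the table and does not result from the CWIT sentence.

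**5. Effect on the analysis.** A within-subjects ANOVA tests for any difference between conditions, so its p-value does not depend on which direction counts as better. The general sentence on analysing each task covers verbal fluency under either grouping.

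**The case for a change.** The strongest opposing case is that the choice of score fixes its variability, and so its power. The planning figures imply a coefficient of variation of 17/47 = 0.36. If the score finally analysed had a coefficient of 0.50, with an assumed within-patient correlation of 0.5, the SD of the difference would equal the SD. The standardised value of a 20% change would then be 0.20/0.50 = 0.40, and power at 30 patients would be about 56%, against about 83% on the tabled figures. An undefined score also leaves room for selection afterwards, and the repair would take only a few sentences.

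Part of this stands. Section 3.0 is wrong as written or the other sections are, and the verbal fluency score is not spelled out. The power loss, however, rests on a hypothetical score. The table labels 47±17 as preliminary verbal fluency data, so the team already had a score for this task when it planned the study, and nothing suggests that it means to analyse another. The scenario in which staff time verbal fluency as if it were a colour-word task requires them to ignore its own calendar slot and its own recorded result.

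**Conclusion.** The concern does not call for a change. It consists of a clerical mislabel in one sentence of Section 3.0 and a missing detail that analysts would fill sensibly. Removing the label and writing down the score would leave the projected 29, the enrolment of 30, the choice of test and its p-value as they are.

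This rests on two readings. The first is that Section 2.0 shows the intended grouping, with verbal fluency in the wider Delis-Kaplan system. The second is that 47±17 and +9.4 are on the scale that will be analysed. The documents do not prove the second, but they contain nothing against it. In a single-centre pilot where each patient is his or her own control, the remaining uncertainty is one of description and does not alter a conclusion.
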